5. RECRUITMENT METHODS

Potential Black and African American participants with and without PD will be ascertained from all of the following:

- Site coordination such as invitation from review of electronic medical records in health systems/Clinical Data Research Networks (CDRNs) and/or databases, and contact with participants of prior research studies who consented to be re-contacted;
- Outreach to community groups, foundations and organizations led by sites and study leadership;
- Self-referrals from public registries such as BLAACPD.org, Fox Trial Finder and clinicaltrials.gov;
- In-person events such as those organized by community groups, foundations, medical centers, and specialty societies;
- In-home visits for interested potential participants who have difficulty with transportation or reside a significant distance away from study sites (Site Permitting)
- Flyers/Bulletins;
- Radio ads;
- Newsletters:
- Social Media posts;
- Through the care-navigation process; and,
- Other tactics to be determined

Basic information about the study eligibility criteria (age, diagnosis of Parkinson's disease, absence of exclusionary criteria) may be determined by the study staff prior to contact with potential participants or by providing potential participants with recruitment materials; site-based contact with potential participants may be during a clinical visit or remotely by telephone. Recruitment materials will be reviewed and approved by the Institutional Review Board (IRB) prior to implementation.

RSRB Study Number: 00006240

Page 11 of 24 Version 5.0

Control participants may also be recruited through above methods (e.g., partners of the participants visiting a clinical neurology department).

Information about recruitment activities may be collected for this study, including but not limited to: the status of potential participants, such as if they have been contacted, if they are undecided about participating, and reasons for declining to participate. Recruitment information will be shared on a regular basis with MJFF.

Recruitment activities, namely primary reason for exclusion, may be tracked to identify primary barriers negatively affecting site recruitment milestones. Recruitment related variables will be collected from Control or PD excluded participants that decline to participate and analyzed to improve study performance by implementing engagement and recruitment strategies.

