From the statistical standpoint, we will explore whether the SIT score is predictive of Parkinson's status in the African admixed population by running a logistic regression analysis, specifying Parkinson's status as the outcome and SIT score as the primary predictive variable of interest. SIT scores will first be normalized to the control mean and standard deviation for the relevant reference population. This helps contextualize the results on to an interpretable scale across populations and place the results in context to understand how an individual's score compares to the general population in terms of standard deviations of change. We will conduct a logistic regression adjusted by gender, age, and principal components to account for population stratification (also on a similar normalized scale). In a stepwise manner, we will prune the initial model to build a more parsimonious model. Finally, we will evaluate the overall fit of the model(s) using metrics like AUC, balanced accuracy and pseudo-R-squared to evaluate the predictive strength of the model(s).

When analyzing SIT scores in the context of PD, a lower score on the test may indicate impaired olfactory function. Olfactory function may be designated as abnormal based on available normative data for age and sex (Brumm, 2023; Doty, 1984). However, the samples on which normative data were generated lack diversity. Smell test data collected from healthy controls in BLAAC PD will be leveraged to improve generalizability of existing normative data to the Black and African American community. From the statistical standpoint, we explore whether the SIT score is predictive of PD status in the African admixed population by running a logistic regression analysis, specifying PD status as the outcome and SIT score as the primary predictive variable of interest. We will conduct logistic regression adjusted by sex, age, and PCs to account for population stratification (on a normalized scale). In a stepwise manner, we will prune the initial model to build a more parsimonious model. Finally, we evaluate the overall fit of the model(s) using metrics like AUC, balanced accuracy and pseudo-R-squared to evaluate the predictive strength of the model(s).

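### The predictive strength of SIT is judged by whole-model metrics that also reward age and sex differences between cases and controls, with no SIT-free model for comparison

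*Protocol*

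**What the plan says.** Two paragraphs of Protocol Section 20 describe the SIT analysis in nearly the same terms. The regression is set up by "specifying Parkinson's status as the outcome and SIT score as the primary predictive variable of interest". The adjustment set follows: "We will conduct a logistic regression adjusted by gender, age, and principal components to account for population stratification". Both paragraphs then say: "In a stepwise manner, we will prune the initial model to build a more parsimonious model". No covariate is named as fixed in the model and no retention rule is given. Both close by relying on "metrics like AUC, balanced accuracy and pseudo-R-squared to evaluate the predictive strength of the model(s").

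Two statements might be thought to deal with age and sex. The first concerns scaling: "SIT scores will first be normalized to the control mean and standard deviation for the relevant reference population". It is not said to be age- or sex-specific. The second is "Olfactory function may be designated as abnormal based on available normative data for age and sex", which concerns labelling a result as abnormal, not the regression or its metrics.

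On who the controls are, Section 4 sets a minimum age of 18 and no other age rule. Section 5 gives as an example of control recruitment "partners of the participants visiting a clinical neurology department". The only matching mentioned is in Section 20: external control data, matched to cases on genetic background.

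**The concern.** The question is about SIT, but the chosen yardsticks belong to a model in which SIT is one of several predictors. In a case-control sample the age and sex make-up of each group is set by recruitment. If controls are younger, or include more women, age and sex separate the groups by themselves, and AUC, balanced accuracy and pseudo-R-squared rise with no help from smell testing. Without the same figures for a model lacking SIT, a reader cannot tell how much of the reported strength is due to SIT. This matters because Section 20 presents olfactory testing as a possible tool for early detection.

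The pruning step raises a second, smaller issue. Age, sex and principal components are in the model to adjust the SIT effect, and the protocol itself cites norms by age and sex for the score. Parsimony is not a reason to remove adjustment variables, and ordinary p-values and confidence intervals from a selected model do not reflect the selection.

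**Working it through.** The protocol states no AUC, sample size or alpha for the SIT analysis, so there is no figure to reproduce. The check is illustrative.

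**From the protocol.** 1,000 to 2,000 per group (Section 3); SIT, age, sex and principal components in the model (Section 20); no age or sex balancing (Sections 4, 5 and 20).

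**Assumed, because the protocol gives no figures.** Age SD 10 years; age gap (cases older) of 0, 1, 5 or 10 years; men in cases/controls 50/50, 50/45, 60/40 or 60/30%; SIT lower by 0.3 SD per decade of age and by 0.25 SD in men; disease effect on SIT of 0 or 1 SD; five principal components unrelated to disease.

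**Step 1: what age or sex alone can do.** For a normal variable with standardised gap d, AUC = Φ(d/√2).
- 5 years: d = 5/10 = 0.5, AUC = Φ(0.354) = 0.64.
- 10 years: d = 10/10 = 1.0, AUC = Φ(0.707) = 0.76.

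For a binary variable, AUC = 0.5 + (difference in proportions)/2.
- 60 v 40% men: 0.5 + 0.20/2 = 0.60.
- 60 v 30% men: 0.5 + 0.30/2 = 0.65.

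**Step 2: whole-model AUC with and without SIT.** Simulation, 60 data sets per scenario, 2,000 per group, in-sample rank-based AUC:

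| Age gap; men in cases/controls | Disease effect on SIT | AUC without SIT | AUC with SIT | Gain |
|---|---|---|---|---|
| 0 y; 50/50% | 0 | 0.524 | 0.526 | 0.00 |
| 0 y; 50/50% | 1 SD | 0.523 | 0.761 | 0.24 |
| 5 y; 60/40% | 0 | 0.676 | 0.676 | 0.00 |
| 5 y; 60/40% | 1 SD | 0.678 | 0.802 | 0.12 |
| 10 y; 60/30% | 0 | 0.799 | 0.799 | 0.00 |
| 10 y; 60/30% | 1 SD | 0.799 | 0.863 | 0.06 |

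With a useless SIT, the planned metric still reaches 0.68 or 0.80. With a fixed 1 SD effect, moving from no imbalance to the 10-year gap raises it from 0.76 to 0.86, while the gain from SIT falls from 0.24 to 0.06. Results at 1,000 per group are nearly the same.

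Reporting the AUC of SIT alone, unadjusted, would not solve this: with no disease effect it was 0.55 and 0.60 in the two imbalanced scenarios. Under the assumed model the age- and sex-adjusted AUC of SIT is Φ(0/√2) = 0.50 with no effect and Φ(1/√2) = 0.76 with a 1 SD effect, whatever the imbalance.

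Scaling SIT to one control mean and SD is a linear change. It leaves fitted probabilities, and so AUC, as they were.

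**Step 3: what pruning would remove.** No rule is given, so dropping is read as p > 0.05 in the full model.
- 5- or 10-year gap: age or sex met this in 0 to 2% of runs. Had both been removed with no disease effect, SIT would have shown a coefficient of -0.18 or -0.34 per SD (odds ratio exp(0.18) = 1.20 or exp(0.34) = about 1.41 per SD lower score).
- 1-year gap, 50/45% men, 1 SD effect: sex met it in 88 to 92% of runs, but with both age and sex out the SIT coefficient moved only from -1.01 to -0.95.
- Null principal components met it in about 95% of runs, as expected; removing these does no harm.

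**The case against.** The best defence is that the text assigns these metrics to the model or models, not to SIT. The question about SIT is put to an adjusted regression, and a useless SIT would show a null coefficient in the initial, unpruned model. That is correct: a reader might infer that the plan credits recruitment differences to smell testing, and the wording does not say so. What stands is that the only stated measures of predictive strength cannot separate SIT from the covariates.

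A reader might also infer that pruning will strip out the confounders and bias the SIT effect. The working does not support that at the planned size: a strongly imbalanced age or sex almost always survives, and removing weakly imbalanced ones changes little. Nor does the protocol say that inference on SIT comes only from the pruned model.

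The imbalances are assumed. Partners may well be close to patients in age, although they could skew sex, and they are only one example among many recruitment routes. With no imbalance the problem almost vanishes (0.53 with a useless SIT).

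It would also be too strong to say that the plan makes an invalid comparison across populations. It rests cross-population interpretation on the scaled score and proposes no comparison of AUCs.

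Finally, the analysis is exploratory, the primary outcome is genetic, and a separate analysis plan could add a comparator. But pruning and whole-model metrics are stated choices in the protocol, each given twice, not details left open.

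**Conclusion.** The point holds for the metrics. As written, AUC, balanced accuracy and pseudo-R-squared of a model containing age, sex and principal components do not answer whether SIT predicts disease status, because nothing in the design balances age or sex and no SIT-free reference is named. Under the assumed imbalances, whole-model AUC is 0.68 to 0.80 with no contribution from SIT. The direction follows from the method; the size depends on imbalances that the protocol neither reports nor prevents.

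The pruning step is secondary. Its practical bias is probably small at 1,000 to 2,000 per group, but it gains nothing for a question about SIT and leaves the usual p-values and intervals ignoring the selection. The adjusted SIT coefficient from the unpruned model is sound. This is a cheap improvement to an exploratory analysis and does not touch the genetic analyses.

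**What to change.** In both SIT paragraphs of Section 20:
- Remove the pruning sentence, state that age, sex and principal components stay in the model, and take inference on SIT from that model.
- Report the AUC of the model with age, sex and principal components only, the AUC with SIT added, and the difference with a bootstrap 95% confidence interval.
- Optionally report the age- and sex-adjusted AUC of SIT. This is the better figure to set beside other cohorts, since the difference itself shrinks as the covariates separate the groups more.
- Base the conclusion about SIT on the difference or the adjusted AUC, not on the whole-model figure.

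The cost is a wording change and a few lines of code on data already being collected. The model is less parsimonious, and the headline figure is likely to be less flattering.

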21. PUBLICATIONS

RSRB Study Number: 00006240

Page 22 of 24 Version 5.0

Publication of results of this study will be governed by the policies and procedures developed by the Global Parkinson's Genetics Program (see publication policy) and in accordance with the International Committee of Medical Journal Editors (ICJME) Uniform Requirements for Manuscripts Submitted to Biomedical Journals. Any presentation, abstract, or manuscript will be made available for review to the Sponsor and GP2 leadership prior to submission.

RSRB Study Number: 00006240

Page 23 of 24 Version 5.0

